## 7 Post-hoc analyses

### 7.1 Estimates of relative risks for binary endpoints

Logistic regression was used for binary secondary endpoints (specifically, adverse events and returning to sports). Since odds ratios are estimated from logistic regression models and since odds ratios may overestimate relative risks, we performed a post-hoc analysis to estimate relative risks for the adverse events and returning to sports secondary endpoints. This was performed according to the following: Marginal relative risks to compare the two treatment arms were calculated starting from a logistic regression including treatment as a covariate and the binary endpoint as the dependent variable, adjusted for age, sex and degree of tendon retraction. Marginal estimates presented are population-averaged adjusted risk ratios and the values are obtained by taking the average of unit-level estimates. Specifically, the marginal relative risks were then calculated by the ratio of the mean predicted risk if all patients were treated nonoperatively to the mean predicted risk if all patients were treated operatively.

### 7.2 Limb symmetry index at 24 months

In a post-hoc analysis, we computed the confidence interval for the limb symmetry index ([value of injured side/value of uninjured side]\*100) for the hamstring muscle volume and fat fraction (measured using MRI) at 24 months *within* the operative and nonoperative groups for both the RCT and observational cohort. Since the LSI is a ratio of two correlated random variables, we used the nonparametric bootstrap (with 10,000 samples) to compute 95% confidence intervals.

## 7.3 Changes to the SAP as a result of the review process

As part of the review process, two main changes were made to the analysis of the trial. Specifically:

1. Instead of using the ITT population for the primary analysis, the PP population was used.
2. Instead of performing analyses where the RCT cohort and the observational cohort were analyzed together, separate analyses were conducted and reported for two cohorts.

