# 1 Revisions

Version	Date	Reason
1.0	May 25, 2017	Version 1.0 developed prior to enrolling first patient in the trial.
1.1	September 19, 2017	Minor clarifications after feedback from clinicians.
1.2	December 4, 2018	Updated sample size.
1.3	June 19, 2022	Finalization of SAP prior to database lock.
1.4	August 30, 2023	Specification of post-hoc analysis to compute relative risks for binary endpoints (Section 7.1).
1.5	January 19, 2024	Specification of post-hoc analysis of limb symmetry index (Section 7.2).
1.6	April 8, 2024	Specification of changes to the SAP as a result of the review process.

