## 3 Introduction

The treatment of proximal hamstring avulsions is controversial. The literature suggests that operative treatment is superior to conservative, non-operative management. However, randomized evidence is lacking. Moreover, few of the existing observational studies have used validated outcome measures, such as Harris Hip Score, the Lower Extremity Functional Scale (LEFS), or the Perth hamstring assessment tool (PHAT).

The Proximal Hamstring Avulsion Clinical Trial (PHACT; NCT03311997) is a prospective, preference tolerant, multicentre, randomised, controlled non-inferiority trial with the aim to provide reliable evidence on how to treat physically active patients, 30–70 years of age, with proximal hamstring avulsions.

The planned analyses identified in this statistical analysis plan (SAP) will be included in future manuscripts. Exploratory analyses not necessarily identified in this SAP may be performed to support planned analyses. Any post-hoc exploratory or unplanned analyses not specified in this SAP will be identified as such in manuscripts for publication, and added as addenda to the SAP. The SAP may be updated during the course of the trial but will be finalized before database lock or any comparative analyses. Any further future analyses not specified in the analysis protocol will be documented in the revision history of this document.

[figure not shown]

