### 4.3 Randomization and blinding

The REDCap (REDCap Software) randomization tool will be used to perform randomization of patients, which will be conducted using a random block size (2-6) stratified by study site.

To minimize ascertainment bias this trial is single-blinded, where the physiotherapist conducting strength and functional tests at 6, 12 and 24 months will be blinded to the intervention, by informing the patients not to tell what group they belong to and asking them to wear clothes concealing potential surgery scar. Statisticians analyzing the data will also be blinded to treatment arms. Consequently, analyses of adverse events will be conducted last (since these are likely to reveal group allocation). Similarly, results will be presented and discussed among investigators prior to analyzing and presenting adverse events (to preserve blinding as long as possible in the construction of the first manuscript from the trial).

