# 5 Analysis of the trial

## 5.1 Analysis populations

The *intention to treat (ITT) population* will consist of all participants randomized and consenting to be part of the study, irrespective of treatment received. Participants in the ITT population will be analyzed according to the treatment they are randomized to, regardless of whether they actually received this treatment or not.

We will also conduct *per-protocol (PP)* and *as-treated (AS)* analyses. Cases will be considered treatment crossovers if the randomly assigned treatment is changed. Non-operative treated patients who are treated operatively due to late complaints (>3 months after inclusion) will in PP and AS analyses be handled in two ways: (i) *not* considered crossovers, in which case we regard these sets of patients as a failed initial conservative treatment strategy, followed by surgery; (ii) considered as cross-overs (analogously to patients who switch groups early, i.e. within 3 months of randomization). The first definition will be employed in the main PP and AS analyzes, whereas the latter will be used in sensitivity analyses (see Section 5.8.4).

The *per protocol (PP) population* will be defined by the participants who were randomized to a specific treatment and received it according to the protocol. Analyses based on the PP population are based on post randomization events (treatment compliance vs. not), which may lead to biased results. We will therefore perform analyses on the PP population using inverse probability weighting to adjust for the effect of these post randomization events. Specifically, let  $A$  be an indicator variable that takes value 1 if the patient was randomized to the surgical arm and 0 if s/he was randomized to the conservative treatment arm. The conditional probability of adhering to the protocol given study arm and other covariates is  $Pr(P=1|Z,A)$ , where  $Z$  is patient covariates (age, sex, site, and degree of tendon retraction). Inverse probability weights of protocol adherence will be defined as  $W=1/Pr(P=1|Z,A)$ . The weights  $W$  will then be used to estimate the contrasts between the operative and non-operative arms using marginal models with a robust (sandwich) standard error estimator according to models specified in Sections 5.2 and 5.3.

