## 5.2 Primary endpoint

PHAT scores (measured at 3, 6, 12, and 24 months) will be assessed and contrasted between the two treatment groups using a linear regression model that adjusts for an indicator of randomized treatment group assignment and for factors used to stratify randomization (site), age, sex, and degree of tendon retraction. The primary analysis will contrast the randomized groups at 24 months in the ITT population (analyses using other follow-up time points are specified in Section 5.8).

Based on the existing literature the standard deviation of PHAT measurements is ~16 – 21. The non-inferiority margin was set to half of the standard deviation (=10). The non-inferiority margin was agreed upon at a consensus group meeting that included orthopedic surgeons and statisticians. The one-sided alpha level will be 0.05. If conservative treatment is non-inferior on the one-sided 0.05 alpha level, we will repeat the test using a one-sided alpha of 0.025.

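### Section 7.3 replaces the pre-specified ITT primary analysis by PP after the SAP was final, without saying why, whether PHAT by arm had been seen, or what status ITT keeps

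*SAP*

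**What the plan says.** Section 5.2 is explicit: "The primary analysis will contrast the randomized groups at 24 months in the ITT population". The margin there is 10 PHAT points, tested at a one-sided alpha of 0.05 and, if that succeeds, again at 0.025.

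Section 3 says that the SAP "will be finalized before database lock or any comparative analyses". The revision table (Section 1) dates this step to version 1.3, June 19, 2022: "Finalization of SAP prior to database lock". Section 3 also covers later additions: "Any post-hoc exploratory or unplanned analyses not specified in this SAP will be identified as such in manuscripts for publication".

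Section 5.1 defines PP as one of two additional analyses, weighted by the inverse probability of adherence given arm, age, sex, site and tendon retraction. It cautions: "Analyses based on the PP population are based on post randomization events (treatment compliance vs. not), which may lead to biased results". Patients in the non-operative arm who are operated on more than 3 months after inclusion are handled in two ways: (i) not as cross-overs, (ii) as cross-overs. On these: "The first definition will be employed in the main PP and AS analyzes, whereas the latter will be used in sensitivity analyses".

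Section 7.3, under the post-hoc heading and belonging to version 1.6 (April 8, 2024), then reports: "Instead of using the ITT population for the primary analysis, the PP population was used".

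**The concern.** The analysis population of the primary endpoint changed after the point at which the SAP says it is final. Section 7.3 leaves three things open:

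- why PP was preferred, and whether the PHAT results by arm had been seen when it was chosen;
- which PP analysis is now primary. The weighted one of Section 5.1 with definition (i) is the natural reading, but 7.3 does not say so;
- what status ITT keeps, and how a disagreement between the two would be reported.

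In a non-inferiority trial with cross-over, ITT and PP can reach different verdicts by chance alone, and each has its own bias. If the primary label moves after results may be known, a reader cannot rule out that the choice followed the results. The main conclusion then depends on which population carries the label.

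**Working it through.** **1. Dates.** June 19, 2022 (version 1.3) to April 8, 2024 (version 1.6) is 659 days; 659 / 30.4375 = 21.7 months. August 30, 2023 (version 1.4) to April 8, 2024 is 222 days, or 7.3 months. These run between version dates. The date of the decision is not given.

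**2. Were results available?** Section 4.3 puts adverse events last, after the other results have been presented to the investigators. Section 7.1, added in version 1.4, describes a between-arm comparison of adverse events in the past tense. If the planned order was kept and that wording dates from version 1.4, PHAT by arm was known before version 1.6. This is inference: the revision table calls version 1.4 a specification, and the tense could have been edited later.

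**3. What could the choice of population do?** The SAP gives no figure for this, so what follows is an illustration.

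*From the SAP:* margin 10, SD 20, one-sided alpha 0.05, 50 evaluable patients per arm (Section 6.2).

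*Assumed:* cross-over proportion p, only out of the non-operative arm, depending on age and retraction; residual bias d; gain g.

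*Models:* ITT is an adjusted linear regression. PP uses adherers only, weighted by 1/Pr(adherence), with a sandwich SE. Both omit site. There were 40,000 simulated trials per no-bias scenario and 20,000 per bias scenario. Mean SE was 4.05 for ITT, and 4.12/4.18/4.34 for PP at p = 5/10/20%.

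*Error* means declaring non-inferiority when the true deficit is 10 points.

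(a) No bias in either analysis:

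| p | ITT error | PP error | Error if either may be named primary | Verdicts differ, no true difference |
|---|---|---|---|---|
| 5% | 4.9% | 5.0% | 5.7% | 4.6% |
| 10% | 4.9% | 5.1% | 6.1% | 6.5% |
| 20% | 4.9% | 5.2% | 6.7% | 10.8% |

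(b) PP alone, if cross-overs would have scored d points lower than weighted adherers. The PP contrast becomes −10 + p·d. Simulated error at p = 10/20%: 6.5/8.1% for d = 5 and 7.9/12.4% for d = 10. With d = −10 it is conservative, at 2.9/2.0%.

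(c) ITT alone, if surgery gives cross-overs g points. The ITT contrast becomes −10 + p·g, so the error is the upper tail of a noncentral t beyond its 5% critical value, with noncentrality p·g/4.05 (95 df assumed, critical value 1.661):
- g = 5, p = 10%: 0.5/4.05 = 0.123, error 6.4%
- g = 5, p = 20%: 1.0/4.05 = 0.247, error 8.1%
- g = 10, p = 10%: 1.0/4.05 = 0.247, error 8.1%
- g = 10, p = 20%: 2.0/4.05 = 0.494, error 12.4%

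These nearly equal the PP figures in (b).

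(d) Both biases present, both analyses required to succeed, p = 10/20%: error 5.0/5.9% at 5 points each and 6.3/9.0% at 10 points each.

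(e) Power with no true difference: ITT alone about 79%; both required, 75.7/74.0/70.9% at p = 5/10/20%.

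**The case against.** The strongest reply is that nothing was hidden. The change is listed in the revision table and sits under the post-hoc heading, which is how Section 3 provides for later additions. PP, its weights and its main cross-over definition were fixed in advance as an additional analysis. ITT has not been deleted: Sections 5.1, 5.2 and 5.5.1 still specify it. All this stands. It does not supply the reason for the change, its timing relative to results, or ITT's remaining status.

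Two stronger readings are tempting, and the SAP supports neither. A reader might infer that PP was chosen because of the PHAT results. The sections compared above make it likely that results were available, but the SAP does not say so, and nothing in it shows that they drove the choice. A reader might also infer that ITT was the sound analysis and PP the flawed one. Steps 3(b) and 3(c) show similar error from either side, so the figures do not justify restoring ITT as the only valid primary analysis.

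The simulation also only approximates the SAP. It leaves out site and the multiple imputation of Section 5.7, and it lets patients leave one arm only. It removes every cross-over from PP, whereas under definition (i) late-operated patients stay in, so some dilution would reach PP too. How the manuscript labels the change cannot be judged from this document.

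**Conclusion.** The point holds as a defect of documentation and interpretation, and it should be fixed. Section 7.3 changes the primary population 659 days after the version 1.3 finalization and leaves the reason, the knowledge of PHAT by arm, the exact PP analysis and the status of ITT unstated.

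The harm specific to switching is modest: error of 5.7–6.7% instead of about 5% at an assumed 5–20% cross-over, with discordant verdicts in about 5–11% of trials when there is no true difference. The larger figures, up to 12.4%, describe the weakness of either population used alone under assumed 10-point biases and 20% cross-over. They are a reason to show both. Confidence is medium, because p, d and g are assumptions and the timing relative to results is inferred.

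A separate, minor inconsistency: the definition (ii) sensitivity analysis is firm in Section 5.1 but optional in Section 5.8.4 on cross-over definitions.

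**What to change.** In Section 7.3:

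1. Identify ITT as the pre-specified primary analysis and PP as its post-hoc replacement. Give the reason, and state whether PHAT by arm had been seen when the change was made. Carry the label into the manuscript, as Section 3 requires.
2. Report the 24-month PHAT contrast in ITT and in weighted PP (definition (i)), each with its confidence interval, side by side and with equal prominence. Leave the weight covariates as pre-specified.
3. Call non-inferiority robust only if both analyses exclude a 10-point deficit at the alpha of Section 5.2, and report any disagreement as such. Present this as a post-hoc conservative reading that does not guarantee 5% error if both biases act.

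In Section 5.8.4 on cross-over definitions, change *may* to *will* to match Section 5.1, so that the definition (ii) analysis is run.

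Cost: one paragraph and one word. Both analyses are already specified and no patients are added. A report that names PP as the only primary analysis would need revision, and the definition (ii) analysis must be run if it has not been. A robust claim becomes harder: about 79% power for ITT alone against 76/74/71% for both at an assumed 5/10/20% cross-over.
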